2.3.2 Study design for subjects with erythrodermic PSO or generalized pustular PSO

2.3.2.1 Period 1: Screening

The Screening Period of 2 to 5 weeks will be used to confirm eligibility and obtain laboratory data.

2.3.2.2 Period 2: Initial Period - Week 0 to Week 16

At least 10 subjects in the cohort with erythrodermic PSO or generalized pustular PSO will be allocated in a 1:1 ratio to the following open-label study treatments:

- CZP 400mg (n ≥ 5): CZP administered sc at the dose of CZP 400mg Q2W
- CZP 200mg (n ≥ 5): CZP administered sc at the dose of CZP 400mg at Weeks 0, 2, and 4, followed by CZP 200mg Q2W (starting at Week 6)

2.3.2.3 Period 3: Maintenance Period - Week 16 to Week 52

The treatment received in Period 3 will be based on the initial study treatment and on response to open-label treatment at Week 16:

- Subjects achieving a “much improved” or “very much improved” in the Global Improvement Score (for subjects with generalized pustular PSO) or a PASI50 response (for subjects with erythrodermic PSO) will continue to receive the same treatment as randomized.
- Subjects in the CZP 200mg Q2W group who are not in response (not achieving “much improved” or “very much improved” in the Global Improvement Score [for subjects with generalized pustular PSO] or a PASI50 response [for subjects with erythrodermic PSO]) will be allowed to have their dose increased to CZP 400mg Q2W, at the discretion of the Investigator. Subjects randomized to CZP 400mg Q2W will continue to receive CZP 400mg Q2W at the discretion of the Investigator. If, in the opinion of the Investigator, the subject is not receiving benefit at the 400mg Q2W dose, the subject could be withdrawn from the study. Per the Withdrawal Criteria, subjects who develop an aggravation of the primary disease or concomitant disease with hospitalization in the opinion of the Investigator must be withdrawn from the study.

2.3.2.4 Period 4: Safety Follow-up: Week 52 to Week 60

All subjects, including those withdrawn from study treatment, will have a Safety Follow-Up Visit, 10 weeks after their final dose of study medication.

2.3.3 Study duration per subject

The study duration for each subject is estimated to be up to 65 weeks as follows:

- Up to 5 weeks of Screening (Period 1)
- 16 weeks in the Initial Period (Period 2)
- 36 weeks in the Maintenance Period (Period 3)
- Safety Follow-Up Visit 10 weeks after final dose of study drug (Period 4)

The end of the study is defined as the date of the final visit of the final subject in the study.

2.3.4 Planned number of subjects, region and sites

Approximately 125 subjects with moderate to severe chronic plaque PSO will be randomized. In addition, a cohort of ≥ 10 subjects with erythrodermic PSO or generalized pustular PSO will be enrolled. The planned number of study sites is approximately 35. The study sites will be located in Japan.

3 DATA ANALYSIS CONSIDERATIONS

3.1 General presentation of summaries and analyses

All statistical analyses will be performed according to Chiltern Standards Operating Procedures using SAS[®] Version 9.3 or higher.

Descriptive statistics will be displayed to provide an overview of the study results. For categorical variables, the number and percentage of subjects in each category will be presented. The denominator for percentages will be based on the number of subjects appropriate for the purpose of analysis for the respective treatment group, subset, period, and visit, if available. Unless otherwise noted, all percentages will be displayed to 1 decimal

place. No decimal will be presented when the percentage is 100%. For data points with $n=0$ (i.e., no subjects in the applicable category), no value for percentage of subjects will be displayed. Missing observations will be included. Thus, percentages always add up to 100% at each visit. For the shift tables, the denominator used for the calculation of percentages will be the number of subjects in the appropriate analysis set.

For continuous variables, descriptive statistics will include number of subjects (n), mean, standard deviation (SD), median, minimum, and maximum. Decimal places for descriptive statistics will always apply the following rules:

- “ n ” will be an integer.
- Mean, SD, and median will use 1 additional decimal place compared to the original data.
- Minimum and maximum will have the same number of decimal places as the original value.

All descriptive statistics will be presented by treatment where applicable, using the available data for the study population as observed. All tabulations will be sorted by treatment, parameter, period and visit (including time relative to dosing if applicable, unless otherwise stated). Only scheduled visits and times relative to dosing will be included in the tabulation. The minimum post-baseline and maximum post-baseline values included in certain analyses by visit are not specific time points; rather they are the minimum and maximum observed non-missing values per subject during PS0017 or in a special period, if appropriate, inclusive of all scheduled and unscheduled visits. If multiple visits fulfill the minimum/maximum criteria, the earlier visit will be flagged to have the minimum/maximum post-baseline value.

The variables will be presented for the subjects with moderate to severe chronic plaque PSO and for the subjects with erythrodermic PSO or generalized pustular PSO, if available, using the appropriate analysis set. Data of the Initial Period and of the Maintenance Period will be tabulated by treatment group and overall. Data of the Maintenance period will also be displayed for the escape arm.

Statistical tests of efficacy variables will be presented as 2-sided p -values rounded to 4 decimal places. P -values less than 0.0001 will be presented as “ <0.0001 ” and p -values greater than 0.9999 will be presented as “ >0.9999 .”

Unless otherwise stated, listings will be sorted by treatment (PBO, then the CZP treatment groups), subject number within treatment group (not randomization number), parameter (if applicable) and visit (if applicable; including timing relative to dosing if applicable). For listings including nonrandomized subjects, the nonrandomized subjects will be shown first in the listing, ordered by subject number. All listings will include repeated and unscheduled measurements; such measurements will appear in chronological order together with the scheduled visits, i.e., a repeated measurement will appear directly after the visit and time relative to dosing, for which the repeat measurement was performed. Data for derived time points Last Visit and Early Withdrawal will also be included in subject data listings. Dates will be presented in the listings in the format ‘YYYY-MM-DD’ and times will be presented in 24h clock format as ‘hh:mm’ or ‘hh:mm:ss’ where appropriate.

3.2 General study level definitions

3.2.1 Analysis time points

All data will be analyzed based on the nominal time points, without mapping to analysis visit windows. If subjects have more than one observation for a given time point, the observation

closest to the intended time point will be used. If both observations are equidistant from the intended time point, then the later value will be used. This rule applies to efficacy data. For safety data, if there is a repeat evaluation, the repeat (latest) data will be used.

The time points for individual assessments are provided in [Table 13–1, Section 13.1](#).

3.2.2 Relative day

The relative day will be calculated for each of the 4 study periods as follows:

Relative day 1 is the date of first study drug (CZP/PBO) administration.

Relative day of date X = date X - Date of first study drug administration +1 if date X is on or after date of first study drug administration and on or before Date of last study drug administration.

Relative day of date X = date X - Date of first study drug administration if date X is before date of first study drug administration.

Relative days before first study drug administration will have the prefix “-”.

Relative day after last dose of study drug administration will have the prefix “+” and will be calculated from the date of last study drug administration (date X - date of last study administration).

Calculations of “Relative Day” should not include partial dates but should be left blank in these instances.

In the case of AEs, relative days for start and stop dates will be calculated as number of days since the first injection of study medication. In addition to the relative days since first injection of study medication, the relative days since the last/latest injection of study medication will be calculated.

3.2.3 Study periods

The end of the study is defined as the date of the last visit of the last subject in the study. Subjects are considered to have completed the study if they completed the Week 52 study visit, not including SFU visit. The study was designed with 4 periods, and data will be assigned to these study periods based on the windows shown in [Table 3–1](#). The label column in this table is the naming convention that will be used to identify the periods included in the analysis tables, figures, and listings. Of particular relevance for this SAP are the Initial Period and the Maintenance Period.

Table 3–1: Study period description and windowing

Period	Description	Label	Window
Period 1	Screening	Screening Period	Up to the date of Randomization - 1 day
Period 2 ^a	16 Week Double-Blind Phase	Initial Period	Date of Randomization to date of Week 16 visit
Period 3	36 Week Double-Blind Phase	Maintenance Period	Date of Week 16 visit +1 day to date of Week 52 visit
Period 4 ^b	8 Week SFU, 10 Weeks after last dose	SFU Period	Date of Week 52 visit +1 day to date of Week 60 visit

^a In general, safety, laboratory and efficacy data collected up to Week 16 of the study belongs to Period 2. The study drug injection at Week 16 and subsequent data collected at future visits (up to Week 52) correspond to Period 3.

^b Or if early discontinuation, date of last visit prior to safety visit +1 day to date of Safety Follow-up visit.

For summaries where the time period from Baseline (Week 0) to Week 52 is of interest, that will be referred to as the Combined Initial and Maintenance Period. A subject will be considered to have completed a period if they complete the last scheduled study visit for that period.

3.2.4 Mapping of assessments performed at Early Discontinuation Visit

Study assessments at an early withdrawal visit will be assigned to the next scheduled site visit following the last visit where assessments were available regardless of if the actual early withdrawal visit date matches another scheduled visit date. The early withdrawal visit re-mapping is not done for pharmacokinetics and anti-CZP antibodies.

3.2.5 Subjects switching centers during the study

Subjects changing center during the study will be allocated to the initial center throughout the study.

3.3 Definition of Baseline values

The last value obtained prior to the first administration of study drug will be used as the baseline value. If there is evidence that measurements taken on the same day as administration of first study medication were actually taken after this administration, then only values strictly prior to that date should be used for that subject.

If a Baseline measurement is missing or not collected, and a Screening value is available, the Screening value will be utilized as the Baseline.

Baseline values for composite scores should be computed using components from the same visit where the relevant measurements were recorded prior to dosing. For example, if the Screening visit has all of the components, but the Baseline visit is missing one or more components, the Baseline value for the component score should be calculated using the Screening visit values.

3.4 Protocol deviations

Important protocol deviations are deviations from the protocol which potentially could have a meaningful impact on study conduct, on the primary efficacy, key safety, or pharmacokinetic (PK)/pharmacodynamic (PD) outcomes for an individual subject. The criteria for identifying important protocol deviations will be defined within the appropriate protocol-specific document. All protocol deviations will be reviewed as part of the ongoing data cleaning process and all important deviations will be identified and documented in a separate Protocol Deviation Tracker prior to unblinding to confirm exclusion from analysis sets.

3.5 Analysis sets

The analysis sets for subjects with moderate to severe chronic plaque PSO are shown below in [Section 3.5.1](#) to [Section 3.5.10](#). The analysis sets for subjects with generalized pustular PSO or erythroid PSO are shown in [Section 3.5.11](#) to [Section 3.5.18](#).

3.5.1 Enrolled Set

The Enrolled Set (ES) will consist of all subjects with plaque PSO who have given informed consent (non-cohort subjects).

3.5.2 Randomized Set

The Randomized Set (RS) will consist of all subjects with plaque PSO randomized into the double-blind part of the study.

3.5.3 Safety Set

The Safety Set (SS) will consist of all subjects in the RS who have received at least 1 dose of study medication.

3.5.4 Full Analysis Set

The Full Analysis Set (FAS) will consist of all subjects in the RS who received at least 1 dose of the study medication and have valid efficacy assessments for baseline and for at least 1 post baseline visit.

3.5.5 Per Protocol Set

The Per-Protocol Set (PPS) will consist of subjects in the FAS who have completed a minimal exposure of 16 weeks to the treatment regimen without any important protocol deviations that may influence the validity of the data for the primary efficacy variable. Important protocol deviations will be predefined and evaluated during a data evaluation meeting prior to unblinding of the data.

The criteria for important protocol deviations leading to exclusion from the PPS will be discussed and appropriately documented (see [Section 3.4](#)).

3.5.6 Pharmacokinetics Per-Protocol Set

The Pharmacokinetics Per-Protocol Set (PK-PPS) will consist of all subjects in the RS who took at least 1 dose of the study medication and provided at least 1 quantifiable CZP plasma concentration while receiving blinded treatment.

The criteria for important protocol deviations leading to exclusion from the PK-PPS will be discussed and appropriately documented (see Section 3.4).

3.5.7 PsA Set

The PsA Set (PsAS) will consist of subjects in the FAS who have PsA disease at Baseline.

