14.4 Planned safety and other analyses

All safety summaries will be performed using the safety set (SS) or Cohort safety set (CSS).

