5 STUDY POPULATION CHARACTERISTICS

5.1 Subject disposition

The number and percentage of screen failures and the primary reason for screen failure will be presented for the ES and CES.

The number of subjects in each analysis set (RS, SS, FAS, PPS, PK-PPS, PsAS and CRS, CSS, CFAS, CPKS, EPS, GPPS) will be presented by investigator, including the dates of the first subject in and the last subject out. The table will be presented overall, by Period (Initial Period and Maintenance Period) and treatment group, for the ES and CES.

Disposition of subjects will be summarized for the RS, PsA Set and CRS by treatment group and overall for the Initial Period. This summary will include the number of subjects that started the period, completed the period, prematurely discontinued study prior to Week 16,

and the reason for discontinuation. A similar summary will be provided for the disposition of subjects in the Maintenance Period by (blinded) maintenance treatment group for the RS and CRS and by escape maintenance treatment group for the Escape Arm on basis of RS.

Subject disposition will be listed for all subjects enrolled and will include the following information: subject status (screen failure, completed or discontinued), date of informed consent, date of randomization, date of first and last dose of study medication (including relative day for last dose, as described in [Section 3.2.2](#)), date of premature study termination (if applicable) and primary reason for study termination (if applicable). The listing will also include the date and reason for breaking the randomization code (if applicable) as well as the date of final contact for the subject. For screen failures the date and reason for screen failure will be listed.

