10.1.1 Interim Analysis

Initial Period

Duration of exposure (days) to study medication, number of days dose received, and patient exposure days at risk during the Initial Period will be summarized by randomized treatment group for the SS, PsAS and CSS. Week 14 is the intended last administration of study medication for this period. The calculations will be as follows:

Duration of exposure:

- Date of last administration of study medication – date of first administration of study medication + 14 days

The 14 days are included in the formula as this is the dosing interval in the Initial Period.

If the date of last administration of study medication + 14 days extends to a date beyond the Week 16 study medication administration date, then this calculation reverts to:

- Week 16 study medication administration date – date of first administration of study medication.

For subjects who die during the Initial Period, if date of last administration of study medication + 14 days extends to a date beyond the date of death, then this calculation reverts to:

- Date of death – date of first administration of study medication +1.

Number of days a dose was received: The total number of dose days from Baseline (Week 0) up to Week 14 (inclusive).

Patient exposure days at risk:

For subjects who complete the Week 16 visit and continue to the Maintenance Period:

- Date of Week 16 administration of study medication – date of first administration of study medication.

For subjects who discontinue on or prior to the Week 16 visit, use the minimum of the following:

- Date of last administration of study medication – date of first administration of study medication + 70 days
- 112 days (equivalent to intended 16-week Initial Period)
- Date of last clinical contact – date of first administration of study medication + 1.

For subjects who die prior to the Week 16 visit:

- Date of death – date of first administration of study medication + 1.

Maintenance Period

Duration of exposure (days) to study medication and number of days dose was received during the Maintenance Period will be summarized by blinded maintenance treatment group for the SS, PsAS and the CSS. Week 22 is the intended last administration of study medication for this period in the interim analysis. The calculations will be as follows:

Duration of exposure:

- Date of last administration of study medication – date of Week 16 administration of study medication + 14 days

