- Major Cardiovascular Events (MACEs). They will be identified using the following SMQs: “Central nervous system haemorrhages and cerebrovascular conditions (SMQ)”, which includes the 3 following sub SMQs: “Conditions associated with central nervous system haemorrhages and cerebrovascular accidents (SMQ)”, “Haemorrhagic central nervous system vascular conditions (SMQ)”, “Ischaemic central nervous system vascular conditions (SMQ)” except events coding to PT “Transient ischaemic attack”. All serious TEAEs which code to a PT included in the HLT “Ischaemic coronary artery disorders” except events coding to PT “Chest Pain” or “Chest discomfort” and all serious TEAEs which code to a PT included in any of the following HLTs: “Heart Failures NEC”, “Left Ventricular Failures”, or “Right Ventricular Failures” and which also code to the SOC of “Cardiac Disorders” as Primary SOC will be included.

AE Summaries by Period

All of the presentations described above will be presented for the Initial Period. Subsets of the presentations described above will be presented for the Maintenance Period and for the Combined Initial and Maintenance Period. Details for these summaries are described below.

Initial Period

Summaries for the Initial Period will be presented by randomized treatment group (PBO, CZP 200mg Q2W, CZP 400mg Q2W, All CZP) based on the SS, PsA Set and the CSS. For these summaries, treatment-emergence is defined as follows:

- For subjects who complete the Week 16 visit and continue to the Maintenance Period, all AEs which started on or after the date of first dose of study medication and on or prior to the date of the Week 16 administration of study medication will be considered a TEAE for these summaries. The only exception to this rule is for the following types of events:
 - Those which code to a HLT of “Injection Site Reactions”
 - Those which have been designated as an Injection Reaction on the AE CRF and do not code to an SOC of “Investigations”
 - Those which have been identified as a hypersensitivity reaction or an anaphylactic reaction

When any of these events occur on the date of treatment switch at Week 16, the AE will be attributed to the treatment initiated at Week 16.

- For subjects who discontinue on or prior to the Week 16 visit, all AEs which started on or after the first dose of study medication and on or prior to the date of last administration of study medication + 70 days will be considered a TEAE for the analysis summaries.

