- For subjects who die prior to the Week 16 visit, all AEs which started on or after the first dose of study medication and prior to or on the date of death will be considered a TEAE for these summaries.

The following AE summaries will be presented:

- Incidence of TEAEs – Overview
- Incidence of TEAEs by TE-ADA status – Overview
- Incidence of TEAEs by TE-ADA status (Includes EAIR and EAER)

- Incidence of TEAEs (includes EAIR and EAER)
- Incidence of Serious TEAEs (includes EAIR and EAER)
- Incidence of TEAEs Resulting in Permanent Discontinuation of Study Drug
- Incidence of TEAEs leading to death
- Incidence of TEAEs by Maximum Intensity
- Incidence of TEAEs by Maximum Relationship
- Incidence of Serious TEAEs by Maximum Relationship
- Incidence of Non-serious TEAEs by Maximum Relationship
- Incidence of TEAEs on or above Reporting Threshold of 5% (not for CSS)
- Incidence of Non-serious TEAEs on or above Reporting Threshold of 5% (not for CSS)
- Incidence of Non-serious TEAEs on or above Reporting Threshold of 5% by Maximum Relationship (not for CSS)
- All AEOI tables

Maintenance Period

The incidence of TEAEs Overview table (open-label) will be provided by treatment group (CZP 200mg Q2W, CZP 400mg Q2W, All CZP) based on the SS. The following AE summaries will be produced considering just those AEs which emerged during the Maintenance Period while on open-label (escape) treatment using the SS and PsAS:

- Incidence of TEAEs – Overview
- Incidence of TEAEs (includes EAIR and EAER)
- Incidence of Serious TEAEs (includes EAIR and EAER)
- Incidence of TEAEs Resulting in Permanent Discontinuation of Study Drug
- Incidence of TEAEs leading to death
- Incidence of TEAEs by Maximum Intensity
- Incidence of TEAEs by Maximum Relationship
- Incidence of TEAEs on or above Reporting Threshold of 5%

Additionally, a listing of TEAEs emerging while on escape treatment will be produced.

Combined Initial and Maintenance Period

Summaries for the Combined Initial and Maintenance Period will be presented by safety treatment group based on the SS, PsAS, and CSS. For these summaries, treatment-emergence is defined as follows:

- For subjects who complete the Week 24 visit, all AEs which started on or after the date of first dose of study medication and on or prior to the date of the Week 24 administration of study medication will be considered a TEAE for the interim analysis summaries.

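### The PsA Set sits inside the Full Analysis Set but is used for PsA adverse event, exposure and disposition tables, so PsA subjects with no post-Baseline efficacy assessment drop out of them

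*SAP*

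**What the plan says.** Three definitions in SAP 3.5 matter.

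- Safety Set (3.5.3): "all subjects in the RS who have received at least 1 dose of study medication". There is no efficacy condition.
- Full Analysis Set (3.5.4): randomized and dosed subjects who also "have valid efficacy assessments for baseline and for at least 1 post baseline visit".
- PsA Set (3.5.7): "The PsA Set (PsAS) will consist of subjects in the FAS who have PsA disease at Baseline". Protocol 14.1 gives the same definition.

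The SAP then uses the PsA Set outside efficacy.

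- Disposition, SAP 5.1: "Disposition of subjects will be summarized for the RS, PsA Set and CRS by treatment group and overall for the Initial Period". This table reports discontinuation before Week 16 and the reason for it.
- Initial Period exposure, SAP 10.1.1: duration, dose days and days at risk "will be summarized by randomized treatment group for the SS, PsAS and CSS". The interim Combined Period exposure names the same three sets.
- Initial Period adverse events, SAP 10.2: presented "based on the SS, PsA Set and the CSS".
- Combined Period adverse events, SAP 10.2: "Summaries for the Combined Initial and Maintenance Period will be presented by safety treatment group based on the SS, PsAS, and CSS".

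Protocol 14.4 makes the Safety Set and the Cohort Safety Set the only populations for safety summaries. SAP 3.9, which lists changes to protocol-defined analyses, says only that the set definitions were clarified.

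**The concern.** Membership of a safety population should depend on having been dosed, and membership of a disposition table on having been randomized. Here both also depend on having given efficacy data after Baseline. Someone who stops very early and does not come back is a person whom a discontinuation table should count. SAP 10.2 defines hypersensitivity reactions by onset on the day of an injection or within one day after it, so such an event can follow the first dose, before any scheduled efficacy visit.

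Elsewhere the SAP keeps the two kinds of set apart. For the pustular and erythrodermic cohort it defines a dose-only Cohort Safety Set (3.5.13) beside an efficacy-conditioned Cohort Full Analysis Set (3.5.14). SAP 6 drops a duplicate table only if the Safety Set equals the FAS, so it allows that they may differ. No PsA subset of the Safety Set or the Randomized Set is defined.

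**Working it through.** The plan states no figure on this point, so there is none to reproduce. The check has two parts.

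**1. Who is lost, and from which tables**

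By definition the PsA Set is inside the FAS, and the FAS is inside the Safety Set.

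- PsA subject, dosed, no valid post-Baseline efficacy: in the Safety Set, not in the FAS, so not in the PsA Set. Missing from PsA adverse event counts, PsA exposure and time at risk, and PsA disposition.
- PsA subject, randomized, not dosed: in the Randomized Set only. Missing from PsA disposition.
- PsA subject who stops early but attends the Withdrawal Visit: Protocol 6.3 requires that visit, Protocol 8.30 includes PASI and PGA at it, and SAP 3.2.4 maps the results to the next scheduled visit. This subject can stay in the FAS and the PsA Set.
- Escape-treatment tables: escape follows failure to reach PASI50 at Week 16, 24, 32 or 40, which presupposes a post-Baseline PASI. The Blinded Maintenance Set (as defined for the interim) and the Escape Maintenance Set also exclude anyone who discontinued in the Initial Period (SAP 3.5.9, 3.5.10). No one of the kind described is lost here.
- Laboratory, vital sign and ECG tables: Safety Set and Cohort Safety Set only, so unaffected.

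**2. Scale and direction, under assumptions**

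The documents give about 125 randomized subjects but neither the number with PsA nor the rate of leaving without post-Baseline efficacy. Protocol 2 mentions PsA in about 30% of psoriasis patients as background, not as an enrolment target. Assumed here: PsA share 10% to 30%; share without post-Baseline efficacy, q, 1% to 5%.

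Expected number lost = 125 × PsA share × q. P(at least one) = 1 − (1 − q)^n, with n rounded to 12, 25 and 38.

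| PsA share (subjects) | q | Expected lost | P(at least one) |
|---|---|---|---|
| 10% (12.5) | 1% | 0.12 | 0.11 |
| 10% (12.5) | 5% | 0.62 | 0.46 |
| 20% (25) | 1% | 0.25 | 0.22 |
| 20% (25) | 2% | 0.50 | 0.40 |
| 30% (37.5) | 2% | 0.75 | 0.54 |
| 30% (37.5) | 5% | 1.88 | 0.86 |

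*Discontinuation.* Dropping k discontinued subjects changes x/n to (x − k)/(n − k), which is lower whenever x < n. With 38 treated PsA subjects and 2 ordinary discontinuations (assumed):

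- one early stop without efficacy data: 2/37 = 5.4% shown instead of 3/38 = 7.9%;
- two such stops: 2/36 = 5.6% shown instead of 4/38 = 10.5%.

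*Adverse events.* Losing a subject who had the event lowers x/n by (n − x)/(n(n − 1)). Under 2:2:1 allocation, a PsA share of 20% to 30% gives about 10 to 15 PsA subjects per CZP arm (25 × 2/5 = 10; 37.5 × 2/5 = 15).

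- Sole event lost: 1/15 = 6.7 points, or 1/10 = 10 points. This is the ceiling.
- One of 8 events in 15 lost: 7/(15 × 14) = 3.3 points.
- Subject without the event lost: 5/15 = 33.3% becomes 5/14 = 35.7%, a rise.

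**The case against.** The strongest defence is that few subjects, if any, will be affected and nothing disappears from the trial. Every dosed subject stays in the overall Safety Set tables and every randomized subject in the overall Randomized Set disposition. The protocol's safety summaries are all still produced; the PsA tables are additional. Protocol 3.3 lists efficacy, not safety, as the PsA objective. The Withdrawal Visit keeps most early leavers in the FAS. All of this stands, and it bounds the size of the problem.

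It also rules out several stronger readings that a reader might infer:

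- *That the earliest discontinuations as a group are removed.* Only those with no post-Baseline efficacy at all are removed, which generally means missing the Withdrawal Visit too.
- *That PsA adverse event rates can only be understated.* This holds for discontinuation. For adverse events it depends on whether the lost subject had the event.
- *That the escape tables lose subjects and that Blinded or Escape Maintenance versions of a new set are needed.* Those sets cannot contain the affected subjects.
- *That final-analysis exposure is explicitly tied to the PsA Set.* SAP 10.1.2 names no analysis set; the PsA Set is named for exposure only in 10.1.1. The PsA adverse event rates in 10.2 do use the time at risk from 10.1.
- *That a definite probability or a typical shift of 7 to 10 points can be quoted.* The probability rests wholly on assumed inputs, and the shift is a ceiling.

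The defence does not explain why a PsA safety or disposition table should carry an efficacy condition.

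**Conclusion.** The point holds for the PsA disposition table of the Initial Period and for the PsA exposure and adverse event tables of the Initial and Combined Periods, with exposure limited to the interim section as written. The set named for them is wrong in kind, is at odds with Protocol 14.4, and is not declared in SAP 3.9. This conclusion rests on the definitions alone and needs no assumed rate.

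The consequence is limited. Most plausibly it is none to about two subjects, on assumptions that the documents cannot confirm. If any are lost, PsA discontinuation is understated and PsA adverse event percentages may go up or down. The primary analysis, all efficacy analyses and the overall safety tables are untouched. It should be corrected because the rule is wrong as written and the correction costs almost nothing, not because a large bias is expected.

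**What to change.** - Add a PsA Safety Set to SAP 3.5: *all subjects in the SS with PsA at Baseline (eCRF)*. SAP 6.2 already takes PsA status from the eCRF.
- Use it in place of the PsA Set for the PsA exposure tables in 10.1.1 and the PsA adverse event tables in 10.2, for the Initial and Combined Periods. State that it also governs the time at risk behind the PsA rates, since 10.1.2 names no set.
- Use Randomized Set subjects with PsA at Baseline for the PsA disposition table in 5.1.
- Keep the FAS-based PsA Set for ACR, DAS28(CRP) and the other efficacy analyses.

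No Blinded Maintenance or Escape Maintenance version is needed. The cost is one set definition, one changed population for disposition, and edits to table titles and footnotes. No new data are required: PsA status is a stratification factor at randomization (Protocol 7.10), so it is known even for subjects who are never dosed.
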